10.4 Definitions of hypoglycaemia

A hypoglycaemic episode will be defined as treatment emergent if the onset of the episode is on or after the first day of randomised treatment and no later than 14 days after the last day of randomised treatment. Hypoglycaemic events will be defined as nocturnal if the time onset is between 00:01 and 05:59 (both included).

A hypoglycaemic episode form and an Adverse Event (AE) form must be filled in for all hypoglycaemic episodes. Hypoglycaemic episodes requiring the assistance of another person to actively administer carbohydrate, glucagon, or other resuscitative actions (i.e., 'severe hypoglycaemic episodes') will be qualified as an event of special interest.

A different definition of hypoglycaemia will apply for patients with type 2 diabetes and a different definition will apply for patients without diabetes.

10.4.1 Classification of hypoglycaemia for participants with type 2 diabetes

All participants with diabetes will be supplied with a glucose meter and a diabetes diary for recording of hypoglycaemia, symptomatic episodes and routine blood glucose monitoring. Plasma glucose should always be measured from all participants with diabetes when there is the suspicion of a hypoglycaemic episode.

All plasma glucose values ≤ 3.1 mmol/L (56mg/dL), as well as values >3.1 mmol/L (56mg/dL) when hypoglycaemic symptoms have occurred should be recorded by the participants in the diaries. Hypoglycaemic episodes will be recorded by the participant in his/her diary throughout the trial and must be transcribed into the CRF by the Investigator at each site visit throughout the trial.

Hypoglycaemic episodes will be summarised based on the American Diabetes Association (ADA) classification and Novo Nordisk's definition.

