10.4.3 ADA hypoglycaemia classification

According to ADA the definition of a hypoglycaemic episode is categorised as:

Severe hypoglycaemia: An episode requiring assistance of another person to actively administer carbohydrate, glucagon, or other resuscitative actions.

Documented symptomatic hypoglycaemia: An episode during which typical symptoms of hypoglycaemia are accompanied by a measured plasma glucose concentration $\leq 3.9 \text{ mmol/L}$.

Asymptomatic hypoglycaemia: An episode not accompanied by typical symptoms of hypoglycaemia, but with a measured plasma glucose concentrations $\leq 3.9 \text{ mmol/L}$.

Probable symptomatic hypoglycaemia: An episode during which symptoms of hypoglycaemia are not accompanied by a plasma glucose determination (but that was presumably caused by a plasma glucose concentration $\leq 3.9 \text{ mmol/L}$).

Relative hypoglycaemia: An episode during which the participant reports any of the typical symptoms of hypoglycaemia and interprets those as indicative of hypoglycaemia, but with a measured plasma glucose concentration $> 3.9 \text{ mmol/L}$.

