Overall hypoglycaemia rate – ADA definition	52, 104	Hypoglycaemia events will be defined as per Appendix 5 for people without

		diabetes and as per the ADA definition in Appendix 5 for people with diabetes. Hypoglycaemia rate will be calculated per participant as total number of hypoglycaemia events divided by the total follow-up time.
Overall hypoglycaemia rate – Novo Nordisk	52, 104	Hypoglycaemia events will be defined as per Appendix 5 for people without diabetes and as per the Novo Nordisk definition in Appendix 5 for people with diabetes. Hypoglycaemia rate will be calculated per participant as total number of hypoglycaemia events divided by the total follow-up time.
AEs	Continual	Defined as in protocol with MEDRA coding used to classify AEs into System Organ Classes
SAEs	52, 104	Defined as in protocol with MEDRA coding used to classify SAEs into System Organ Classes
Rates of severe hypoglycaemia	52, 104	Calculated per participant as total number of severe hypoglycaemia events divided by the total follow-up time, where severe hypoglycaemia is defined as hypoglycaemic episodes requiring the assistance of another person to actively administer carbohydrate, glucagon, or other resuscitative actions (i.e., 'severe hypoglycaemic episodes')
Change in heart rate from baseline (beats per minute)	52, 104	Follow-up heart rate – baseline heart rate
Compliance of patient with the treatment		
Compliant with Tier 3 service (completers)	52, 104	Binary indicator of 1 if participant is compliant, 0 otherwise (defined in study database)
Stopped treatment with LIRA 3mg because of adverse effects	52, 104	Binary indicator of 1 if participant stopped treatment with LIRA 3mg because of adverse effects*, 0 otherwise. Only defined for participants in intervention arm who were currently eligible for LIRA 3mg treatment. * This includes main reason of 'adverse event' or 'unable to tolerate drug'.
The adherence of participants with the LIRA	52, 104	Participants will be defined as treatment compliant if they self-administer at least 70% of planned doses. Binary indicator of 1 if participant is compliant, 0 otherwise.

3mg (monitored through specific questionnaire and return of used pens)		Given the change in visits as a result of COVID-19 to allow face-to-face, this will be defined using the questionnaire answers as detailed in Appendix 7. Only defined for participants in intervention arm who were currently eligible for LIRA 3mg treatment.

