- An episode with symptoms consistent with hypoglycaemia with confirmation by plasma glucose < 3.1 mmol/L (56 mg/dL), or full blood glucose < 2.8 mmol/L (50 mg/dL) and which is handled by the subject himself/herself

- Or any asymptomatic plasma glucose value < 3.1 mmol/L (56 mg/dL) or full blood glucose value < 2.8 mmol/L (50 mg/dL). Minor hypoglycaemic episodes will be summarised according to this definition, and can be subject to additional analysis.

ADA hypoglycaemia classification

According to ADA the definition of a hypoglycaemic episode is categorised as:

Severe hypoglycaemia: An episode requiring assistance of another person to actively administer carbohydrate, glucagon, or other resuscitative actions.

Documented symptomatic hypoglycaemia: An episode during which typical symptoms of hypoglycaemia are accompanied by a measured plasma glucose concentration ≤ 3.9 mmol/L.

Asymptomatic hypoglycaemia: An episode not accompanied by typical symptoms of hypoglycaemia, but with a measured plasma glucose concentrations ≤ 3.9 mmol/L.

Probable symptomatic hypoglycaemia: An episode during which symptoms of hypoglycaemia are not accompanied by a plasma glucose determination (but that was presumably caused by a plasma glucose concentration ≤ 3.9 mmol/L).

Relative hypoglycaemia: An episode during which the participant reports any of the typical symptoms of hypoglycaemia and interprets those as indicative of hypoglycaemia, but with a measured plasma glucose concentration > 3.9 mmol/L.

Classification of hypoglycaemia for participants without diabetes

Participants without diabetes will not be routinely provided with blood glucose meters or diaries; hence blood glucose will not be measured in case of symptoms of hypoglycaemia unless it coincides with a clinic visit.

The hypoglycaemia events for participants without diabetes will be reported spontaneously i.e., symptoms of hypoglycaemia (not biochemically confirmed) occurring outside of visits to the clinic; severe hypoglycaemia will be defined as an episode requiring assistance of another person to actively administer carbohydrate, glucagon, or other resuscitative actions. In the event of severe or symptomatic hypoglycaemia patients will be given a glucose monitor and asked to record their blood glucose whenever they feel symptomatic.

13 Appendix 6: IPAQ scoring system

Further details including data processing rules can be found here:

<https://sites.google.com/site/theipaq/scoring-protocol>

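### In participants with diabetes, symptom-free glucose values above 3.1 and up to 3.9 mmol/L count as ADA hypoglycaemia but need not be recorded, so the overall ADA rate is liable to be undercounted

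*Protocol*

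**What the plan says.** Protocol 10.4.1 sets the diary rule for participants with type 2 diabetes: "All plasma glucose values ≤ 3.1 mmol/L (56mg/dL), as well as values >3.1 mmol/L (56mg/dL"), the latter "when hypoglycaemic symptoms have occurred should be recorded by the participants in the diaries". SAP Appendix 5 repeats the rule unchanged. Section 10.4.1 also says that diary episodes are transcribed into the CRF at site visits, and names two classifications for reporting: "Hypoglycaemic episodes will be summarised based on the American Diabetes Association (ADA) classification and Novo Nordisk's definition".

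The ADA asymptomatic category, in protocol 10.4.3 and again in SAP Appendix 5, is "An episode not accompanied by typical symptoms of hypoglycaemia, but with a measured plasma glucose concentrations ≤ 3.9 mmol/L". The Novo Nordisk definition of a minor episode (protocol 10.4.2) uses plasma glucose below 3.1 mmol/L, with or without symptoms.

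SAP 2.2.1 lists "Overall hypoglycaemia rate – ADA definition" as a safety endpoint at 52 and 104 weeks. Events are defined "as per the ADA definition in Appendix 5 for people with diabetes", and each participant's rate is the number of events divided by follow-up time. No ADA category is left out of the count. SAP 16.13 gives the rate its own table rows, and SAP section 6 tabulates hypoglycaemia by glycaemic status under each definition separately. SAP 5.8, which lists changes to the planned analysis, does not mention the recording threshold.

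**The concern.** The recording rule fits one of the two classifications it has to serve. It covers the Novo Nordisk cut-off in full, but stops 0.8 mmol/L short of the ADA cut-off for values without symptoms. Such a value is an event under the SAP, yet the participant who sees it at home is not told to write it down.

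At stake is whether a named safety outcome means what its label says. A reader of the tables would take the ADA rate to cover the whole classification. The comparison of the two definitions is also affected, because the recording rule supports one of them completely and the other only in part.

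**Working it through.** The plan gives no figure to reproduce, so the check sets the rule against the categories.

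**Thresholds.** With 1 mmol/L = 18.016 mg/dL, 3.1 mmol/L is 55.8 mg/dL (the protocol gives 56) and 3.9 mmol/L is 70.3 mg/dL. The band without an explicit recording rule is above 3.1 and up to 3.9 mmol/L, or 3.9 − 3.1 = 0.8 mmol/L wide.

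**Which events the rule covers (participants with diabetes).**

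| Event | Defining condition | Affected by the threshold? |
|---|---|---|
| ADA severe | Help from another person needed | No: not defined by a glucose value |
| ADA documented symptomatic | Symptoms, ≤3.9 | No: symptomatic values are recorded at any level |
| ADA asymptomatic | No symptoms, ≤3.9 | Yes: required at ≤3.1, not required above 3.1 and up to 3.9 |
| ADA probable symptomatic | Symptoms, no measurement | No: no glucose value involved |
| ADA relative | Symptoms, >3.9 | No: symptomatic values above 3.1 are recorded |
| Novo Nordisk minor | <3.1, with or without symptoms | No: the ≤3.1 rule covers it |

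One of the five ADA categories is affected. Participants without diabetes have no routine meter or diary (protocol 10.4.4), so the rule does not apply to them.

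**Direction.** Missing entries can only remove events. The error is an undercount, or zero if every value in the band is recorded anyway.

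**Size, for illustration only.** Let a be the asymptomatic share of all ADA episodes, g the share of those lying above 3.1 and up to 3.9 mmol/L, and c the share of these that reach the diary regardless. If all other episodes are fully captured, the missing share of ADA episodes is a × g × (1 − c). The documents give none of the three. Assuming a between 10% and 50% and g between 50% and 80%:

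- c = 0: 0.10 × 0.50 = 5% to 0.50 × 0.80 = 40%
- c = 0.5: half of that, 2.5% to 20%
- c = 1: 0

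The spread shows how little can be said about size. It is not an estimate for this trial.

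**The case against.** The strongest reply is that the diary rule is a minimum list. Section 10.4.1 says the diary also serves routine glucose monitoring, and section 10.4 asks for an episode form and an adverse event form for every hypoglycaemic episode, with no threshold attached. Some or all values in the band may therefore be on file. This stands as far as it goes: a reader might infer that all such values are lost, and the documents do not support that. It does not close the gap. No monitoring frequency and no 3.9 mmol/L recording instruction is given, so capture rests on individual habit. A site can complete a form only for an episode it learns of, and for a symptom-free value at home its source is the diary.

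A reader might also infer that the asymptomatic category is missing over most of its range. As a matter of scale, 0.8 of 3.9 mmol/L is about 21%; as a matter of episodes, the documents give no distribution.

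It is also fair to say that little turns on this. Insulin-treated participants are excluded (protocol 7.3). Hypoglycaemia risk is described as low, though possibly higher with sulphonylureas (14.10.1), and section 8.10 refers to a small number of participants with diabetes. The outcome is tabulated without a formal test, and the rule is the same in both arms. These points limit the importance of the gap; they do not make the label accurate.

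**Conclusion.** The mismatch is in the current text of both documents and feeds a planned safety endpoint. In participants with type 2 diabetes, symptom-free values above 3.1 and up to 3.9 mmol/L count towards the overall ADA rate but are not required to be recorded. The rate is liable to be undercounted by an amount that cannot be derived from the documents; the 0 to 40% shown in the working rests wholly on assumed inputs.

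The conclusion assumes that the CRF data for these episodes come mainly from the diary, which is the route section 10.4.1 describes. It does not extend to the ADA classification as a whole, to the severe hypoglycaemia rate or to the primary outcome. Nor does the rule by itself imply a bias between the arms. This is a gap in collection and labelling for one secondary safety outcome, worth correcting because the correction costs almost nothing.

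**What to change.** **Where data are still being collected:** reconcile the diary instruction in protocol 10.4.1 and SAP Appendix 5 with the ADA category, so that all values at or below 3.9 mmol/L are recorded. This probably comes too late for most or all of this trial: the amendment history gives a study end date of 30/06/2022, and the draft SAP is dated 01/08/2022.

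**For data already collected:** amend the SAP before database lock, the point by which its introduction says it will be finalised.

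1. In SAP 2.2.1 and the table in 16.13, report ADA asymptomatic episodes in a separate row, split at 3.1 mmol/L. Label the part above 3.1 and up to 3.9 as not systematically collected.
2. Present the overall ADA rate both with and without the asymptomatic category. The version without it uses only categories that the threshold leaves untouched. The version with it keeps the readings at or below 3.1 that the rule does require.
3. Add a footnote on the incomplete capture, and carry it to the tabulation by glycaemic status in SAP section 6.

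The split needs the glucose value for each episode, which the ADA classification already requires. The documents mention no meter downloads, so the fix does not rely on them. The cost is one or two extra table rows, a footnote, and an ADA rate that looks less complete. If the diary instruction is changed, participants with diabetes make slightly more entries.

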10.4.2 Novo Nordisk definition

In normal physiology, hypoglycaemia symptoms occur at a blood glucose level of approximately $< 2.8 \text{ mmol/L (50 mg/dL)}$ /plasma glucose level $< 3.1 \text{ mmol/L (56 mg/dL)}$. Therefore, Novo Nordisk has used this cut-off value to define minor hypoglycaemia.

Minor hypoglycaemic episode is defined as:

- An episode with symptoms consistent with hypoglycaemia with confirmation by plasma glucose $< 3.1 \text{ mmol/L (56 mg/dL)}$, or full blood glucose $< 2.8 \text{ mmol/L (50 mg/dL)}$ and which is handled by the subject himself/herself
- Or any asymptomatic plasma glucose value $< 3.1 \text{ mmol/L (56 mg/dL)}$ or full blood glucose value $< 2.8 \text{ mmol/L (50 mg/dL)}$ Minor hypoglycaemic episodes will be summarised according to this definition, and can be subject to additional analysis.

10.4.3 ADA hypoglycaemia classification

According to ADA the definition of a hypoglycaemic episode is categorised as:

Severe hypoglycaemia: An episode requiring assistance of another person to actively administer carbohydrate, glucagon, or other resuscitative actions.

Documented symptomatic hypoglycaemia: An episode during which typical symptoms of hypoglycaemia are accompanied by a measured plasma glucose concentration $\leq 3.9 \text{ mmol/L}$.

Asymptomatic hypoglycaemia: An episode not accompanied by typical symptoms of hypoglycaemia, but with a measured plasma glucose concentrations $\leq 3.9 \text{ mmol/L}$.

Probable symptomatic hypoglycaemia: An episode during which symptoms of hypoglycaemia are not accompanied by a plasma glucose determination (but that was presumably caused by a plasma glucose concentration $\leq 3.9 \text{ mmol/L}$).

Relative hypoglycaemia: An episode during which the participant reports any of the typical symptoms of hypoglycaemia and interprets those as indicative of hypoglycaemia, but with a measured plasma glucose concentration $> 3.9 \text{ mmol/L}$.

10.4.4 Classification of hypoglycaemia for participants without diabetes

Participants without diabetes will not be routinely provided with blood glucose meters or diaries; hence blood glucose will not be measured in case of symptoms of hypoglycaemia unless it coincides with a clinic visit.

The hypoglycaemia events for participants without diabetes will be reported spontaneously i.e., symptoms of hypoglycaemia (not biochemically confirmed) occurring outside of visits to the clinic; severe hypoglycaemia will be defined as an episode requiring assistance of another person to actively administer carbohydrate, glucagon, or other resuscitative actions. In the event of severe or

symptomatic hypoglycaemia patients will be given a glucose monitor and asked to record their blood glucose whenever they feel symptomatic.

10.5 Reporting Procedures for All Adverse Events

All pregnancies, AEs, ARs, UARs, SAEs or SARs occurring during the study observed by the investigator or reported by the participant, whether or not attributed to study medication, will be recorded on the CRF and the medical notes. They will be reported in accordance with the Sponsor, host organisation, Novo Nordisk procedures, policies and requirements.

The following information will be recorded: description, date of onset and end date, severity, assessment of relatedness to study medication, other suspect drug or device and action taken. Follow-up information should be provided as necessary.

AEs considered related to the study medication as judged by a medically qualified investigator or the Sponsor will be followed until resolution or the event is considered stable. All related AEs that result in a participant's withdrawal from the study or are present at the end of the study, should be followed up until a satisfactory resolution occurs.

It will be left to the investigator's clinical judgment whether or not an AE is of sufficient severity to require the participant's removal from treatment (see section 10.1 and 10.2). A participant may also voluntarily withdraw from treatment due to what he or she perceives as an intolerable AE. If either of these occurs, the participant must undergo an end of study assessment and be given appropriate care under medical supervision until symptoms cease or the condition becomes stable.

The severity of events will be assessed on the following scale: 1 = mild, 2 = moderate, 3 = severe.

The relationship of AEs to the study medication will be assessed by a medically qualified investigator.

10.6 Pregnancy

Participants must be instructed to notify the Investigator immediately if they become pregnant during the trial. The Investigator must report any pregnancy during the trial to Novo Nordisk except for pregnancies occurring in the screening period prior to study treatment. Participants will give consent on enrolment that the Investigator will report any pregnancy during the trial to Novo Nordisk and they will be asked to provide information about the pregnancy, delivery and the health of her infant until one month of age. The Investigator must report information on pregnancy and follow-up according to Sponsor and local guidelines. If the pregnancy results in an abnormal outcome, such as congenital abnormalities, foetal death, spontaneous abortion, or SAE in the neonate, this should be regarded as an SAE with the same reporting requirements and timelines as for SAEs. If an SAE occurs in relation to a pregnancy, either to the mother or the newborn, then follow the same reporting requirements and timelines as for SAEs.

10.7 Follow-up of Adverse Events

During and following a patient's participation in the study, the Investigator will ensure that adequate medical care is provided to the participant for any AEs, including clinically significant laboratory

values related to the trial. The Investigator will inform the participant when medical care is needed for AE(s) of which the Investigator becomes aware.

The follow-up information will only include new (updated and/or additional) information that reflects the situation at the time of the Investigator's signature.

All serious AEs and all non-serious AEs classified as severe or possibly/probably related to the trial product will be followed-up until the participant has recovered, recovered with sequelae or fatal and until all queries have been resolved. For cases of chronic conditions or if the participant dies from another event, follow-up until the outcome category is "recovered" is not required, as these cases can be closed with an outcome of "recovering" or "not recovered".

The Sponsor guidance and processes for reporting SAEs will be adhered to.

10.8 Reporting Procedures for Serious Adverse Events

All SAEs must be reported to the Sponsor within 24 hours of discovery or notification of the event. The Sponsor will perform an initial check of the information and ensure that it is reviewed at the next R&I Management meeting. All SAE information must be recorded on a current CTIMP SAE form and sent to the Sponsor. Additional information received for a case (follow-up or corrections to the original case) needs to be detailed on a new SAE form and sent to the Sponsor. All SAEs that are at least possibly related to the study treatment – Serious Adverse Reactions (SAR) – still present at the end of the study will be followed at least until the final outcome is determined. Even if it implies that the follow-up continues after the participants leave the trial and when appropriate until the end of the planned period of follow-up.

The Sponsor will report all SUSARs to both the Competent Authorities (MHRA in the UK, HPRA in Ireland) and the Research Ethics Committee concerned. Fatal or life-threatening SUSARs must be reported within 7 days and all other SUSARs within 15 days. The CI will inform all investigators concerned of relevant information about SUSARs that could adversely affect the safety of participants.

The CI will copy Novo Nordisk into communications about SAEs, SARs and SUSARs when expediting to the Sponsor, health and regulatory authorities.

In addition to the expedited reporting above, within 90 days following the anniversary of the authorisation date for the study a Development Safety Update Reports (DSURs) will be sent by the Chief Investigator to the MHRA, HPRA and the Main Research Ethics Committee. A copy of the report will also be sent to Novo Nordisk (as the study funder), the University of Leicester (as the study Sponsor), and all host organisations.

